Dental Appliance for Parkinson Disease (DAPD)

Official Title: Dental Appliance for Parkinson's Disease

NCT Number: 04082663

Document Date: April 23, 2019

I. SPECIFIC AIMS

The primary objective of this study is to determine if the use of a dental mouthpiece can improve gait and motor signs and symptoms, sleep, or quality of life for people with Parkinson's disease (PD). We will conduct a pilot study with participants who have been diagnosed with PD recruited from the community. For this study, participants will have one in-person study visit where they will be fitted with a dental mouthpiece and complete motor tests while wearing the mouthpiece and while not wearing the mouthpiece. Participants will also complete sleep questionnaires and quality of life questionnaires. Participants will then be asked to take the mouthpiece home and wear it at night while they sleep and during the day, except while eating, for one month. At the end of the month, they will complete the same sleep and quality of life questionnaires administered remotely by mail and answer questions about their experience with the dental mouthpiece.

Specific Aim 1: To determine the immediate effect of a dental mouthpiece on Parkinsonian gait and motor symptoms. A 4.8m GAITRite (CIR Systems, Inc., Franklin, NJ) will be utilized to quantify gait mechanics with and without mouthpiece use. Gait and balance tasks will be assessed.

Hypotheses:

- a. People with PD will show improvements in gait speed with the mouthpiece in place compared to without.
- b. People with PD will show improvements in balance with the mouthpiece in place compared to without.

Specific Aim 2: To determine the longer-term feasibility of use and effect of dental mouthpiece on sleep and quality of life (QOL) for people with PD.

Hypotheses:

- a. People with PD will show improvements in sleep quality and duration after one month of wearing the mouthpiece as compared to baseline.
- b. People with PD will show improvements in health-related quality of life after one month of wearing the mouthpiece as compared to baseline.

II. BACKGROUND AND SIGNIFICANCE

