- (4) freezing of gait which moderately or severely impacts walking; or
- (5) current use of an oral appliance (e.g., a dental mouthpiece, retainer, or braces).

Measures and Materials

The MMSE will be administered to ensure absence of cognitive impairment. The New Freezing of Gait Questionnaire (nFOG) includes participants watching a short video about freezing of gait and a questionnaire about whether they experience freezing of gait and if so, questions that help describe the types of freezing of gait they experience.

Mouthpiece

Each participant will be fitted with a maxillary orthotic (mouthpiece) fabricated by [name]. The process for fabrication of the mouthpiece will be as follows:

- 1) The participant is seated in a normal straight-backed chair with feet on the floor.
- 2) A dental impression tray is sized appropriately for the participant's lower jaw to ensure that no impingement of soft tissue structures occurs.
- 3) A quick setting dental alginate impression material is mixed for one minute and then placed into the dental impression tray.
- 4) The dental impression tray is filled with the alginate material, and the tray and material are placed into the participant's mouth.
- 5) The tray will remain in the mouth approximately 1 to 2 minutes and will then be removed.
- 6) A fast setting dental stone is placed in the tray.
- 7) The dental stone is allowed to set for one-half hour in the alginate impression.
- 8) The dental stone model is removed from the alginate impression.
- 9) The lower jaw model is trimmed and then taken to the dental vacuum former machine where a poly-vinyl-acetate (medical-dental grade) thermoplastic sheet of material is heated to a temperature to allow deformation of the material.

- 10) The vacuum is turned on and the thermoplastic material is sucked down over the dental stone model. A small 5 mm wide strip of thermoplastic material is placed directly over the occlusal portion of all the mandibular teeth to act as a reinforcement.
- 11) The thermoplastic material is cooled to below room temperature with cold water until stiff.
- 12) All thermoplastic material which approximates any structure but the dental hard tissue (teeth) is removed from a height just above the attached gingival tissue so that the mouthpiece will be entirely tooth borne.

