Participants will keep a journal documenting how long they wore the mouthpiece at night and during the day, reasons for taking it out, and can make comments about the mouthpiece.

Exit questionnaires

Participants will complete an open-ended exit questionnaire regarding their experience with the mouthpiece and the Global Rate of Change Scale (GRC) after wearing the mouthpiece for one month.

Protocol

A phone screen will be used to screen for preliminary study suitability. If the potential participant passes the phone screen and would like to enroll in the study, we will then schedule them for their in-person visit.

The first visit will be in-person on the ground floor of the Movement Science Research Center at [name]. The study visit will follow the following schedule:

Informed consent, MMSE, nFOG (15 minutes): A trained researcher will review the informed consent document with the participant, outlining the study objectives and ensuring the participants have the opportunity to ask the researcher any questions they may have regarding the study and procedures. If the participant wants to continue, they will sign the consent form. The MMSE will be performed to screen for cognitive impairments which would affect study participation. The nFOG will provide us with information about freezing of gait if applicable.

Motor Assessment #1 without mouthpiece (45 minutes): MDS-UPDRS-III, GAITRite, Mini-Bestest (order will be randomized)

Dental Measurements (15 minutes): [name] will take dental measurements for the purpose of creating a custom-fitted mouthpiece as outlined in the Methods section.

Questionnaires, Medical History, Medications (30 minutes): The participants will complete demographic, medical history/medications forms, sleep and quality of life questionnaires while their mouthpiece is being fabricated.

Mouthpiece in (25 minutes): After their mouthpiece has been fabricated and adjusted (smoothed as needed), participants will sit with the mouthpiece in for 25 minutes.

Motor Assessment #2 with mouthpiece (45 minutes): MDS-UPDRS-III, GAITRite, Mini-Bestest, (order will be randomized)

Participants who take medication for Parkinson symptoms, will be asked to take their medication 30 minutes before arrival to ensure participants are in the "on" phase for the motor tasks.

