At completion of the in-person visit, participants will be instructed to use the mouthpiece as much as possible for the next month. Participants will be informed they can take the mouthpiece out while eating and will be instructed to keep track of how long they wear the mouthpiece each day by journal entry.

Follow-up will occur one month later.

Questionnaires, Medical History, Medications (30 minutes): The participants will complete sleep and quality of life questionnaires, record any changes in their medical history or medications, and complete an open-ended questionnaire regarding their thoughts on the mouthpiece and the GRC.

Randomization Method

The order in which the motor assessments are given in regards to wearing the mouthpiece or not will be randomized for each participant. The motor tasks (disease severity, gait, balance) will be randomized within each participant.

Safety and Adverse Events

The research team will do everything possible to ensure safety of all participants over the course of this study. The adverse event most likely to occur in this study is risk of falling while walking. Participants will be fitted with a gait belt. Members of the research team are trained in fall prevention and will closely monitor all participants throughout all aspects of the study in case of a need to assist with balance to prevent a fall. In the case of an adverse event, emergency medical care will be sought immediately if needed. Any serious adverse events will be reported to the local IRB immediately. Occurrence of an adverse event will be noted in a participant's file.

Potential risks will be addressed in the following ways:

- a) Discomfort in answering questionnaires: Participants may refuse to answer any questions they prefer not to answer.
- b) Loss of confidentiality: Loss of confidentiality is highly unlikely. To safeguard against this, we will comply with all HIPAA regulations. Data will not be identified by participant name. All data will be coded, and code sheets will be stored in locked files.
- c) Stumbling during locomotion: Participants will be closely attended by a trained research staff member during walking and fitted with a gait belt. Walking will be performed in a large, open space and the staff member will be prepared to assist participants who may stumble.

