- d) Falling: Participants will be closely attended by a trained assistant who will ensure the safest of conditions. It is unlikely that participants will experience falls during testing or will be injured as the result of a fall. If a participant appears unsteady, breaks will be encouraged or testing will be terminated.
- e) Fatigue from walking: Rest breaks will be provided as needed.

Dental Appliance for Parkinson Disease (DAPD)

f) Discomfort or irritation while being fitted for the mouthpiece or while wearing the mouthpiece: the participants may remove the mouthpiece at any time.

Benefits

We do not yet know the full extent to which the mouthpiece may improve symptoms associated with Parkinson disease. This study may help inform future treatment techniques to improve motor and non-motor function in people with PD.

Interim Monitoring and Early Stopping

Data will be monitored throughout the study and, should any issues arise, we will adjust our protocol and submit any changes to the IRB project for review. We will not conduct interim data analyses.

Statistical Analyses Plan

We will use paired t-tests to determine if there are differences between conditions (with mouthpiece vs without mouthpiece). We will also use paired t-tests to compare sleep and quality of life questionnaires from baseline (prior to study) to follow up (after one month of mouthpiece use).

R will be used for data analysis across all aims.

Power

Because of the exploratory nature of this pilot study and relative lack of information in the literature, no formal power analysis was conducted.

References:

- 2. Shulman LM. Understanding disability in Parkinson's disease. Mov Disord 2010;25 Suppl 1:S131-5.
- 4. Ellis TD C, JT, Earhart GM, Ford MP, Foreman KB, Thackeray A, Thiese MS, Dibble LE. Identifying clinical measures that most accurately reflect the progression of disability in Parkinson disease. Parkinsonism Relat Disord 2016;25:65-71.

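### Mouthpiece order is said to be randomized, but the visit schedule always tests without it first, so Aim 1 cannot separate the mouthpiece from the passage of time

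*Combined protocol and SAP*

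**What the plan says.** Randomization Method (III. Methods) states: "The order in which the motor assessments are given in regards to wearing the mouthpiece or not will be randomized for each participant". The sentence after it deals separately with the order of the three motor tasks, so the quoted sentence cannot be read as meaning task order only.

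Protocol (III. Methods) gives a single visit schedule:

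- It lists "Motor Assessment #1 without mouthpiece (45 minutes): MDS-UPDRS-III, GAITRite, Mini-Bestest (order will be randomized"). The randomization named here is of the three tests within the assessment.
- Dental measurements come next. Participants then complete forms, including "sleep and quality of life questionnaires while their mouthpiece is being fabricated".
- "After their mouthpiece has been fabricated and adjusted (smoothed as needed), participants will sit with the mouthpiece in for 25 minutes".
- The visit ends with "Motor Assessment #2 with mouthpiece (45 minutes").

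The Mouthpiece subsection, step 7, says: "The dental stone is allowed to set for one-half hour in the alginate impression". Specific Aims says "participants will have one in-person study visit where they will be fitted with a dental mouthpiece and complete motor tests", so there is no earlier visit at which the device could be made.

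For Aim 1 the Statistical Analyses Plan says: "We will use paired t-tests to determine if there are differences between conditions (with mouthpiece vs without mouthpiece"). It has no period or sequence term. The Power paragraph says no power analysis was done, and no sample size is given anywhere.

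**The concern.** The plan claims control of order that its own schedule cannot deliver. Aim 1 asks about the immediate effect of the mouthpiece on gait, balance and motor signs. If the device is always worn at the second assessment, anything that changes between the first and second assessments enters the with-minus-without difference. Obvious candidates are familiarity with the tests, tiredness and the time elapsed since medication.

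A significant paired difference could then appear with no mouthpiece effect, and a real effect could be cancelled. Someone relying on the Randomization Method section would think order had been dealt with and would credit the difference to the mouthpiece. Only Aim 1 is affected. The one-month questionnaire comparisons in Aim 2 do not depend on this order.

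**Working it through.** The plan states no sample size, power or error rate, so there is no figure of its own to reproduce.

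**Step 1. Timeline.** Durations are from the Protocol section; medication is taken 30 minutes before arrival.

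| Block | Length (min) | Minutes after dose |
|---|---|---|
| Consent, MMSE, nFOG | 15 | 30–45 |
| Assessment #1, without | 45 | 45–90 |
| Dental measurements | 15 | 90–105 |
| Questionnaires, device being made | 30 | 105–135 |
| Mouthpiece in, seated | 25 | 135–160 |
| Assessment #2, with | 45 | 160–205 |

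The visit totals 15 + 45 + 15 + 30 + 25 + 45 = 175 minutes, and the assessment starts are 160 − 45 = 115 minutes apart. These are sums of the listed blocks. Stone setting alone fills the 30-minute block, so trimming, forming, adjustment and any rest breaks would lengthen the gap.

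**Step 2. Could the mouthpiece come first?** Before Assessment #1 there are 15 minutes. The device needs 15 minutes of measurements plus at least 30 minutes of stone setting. On this schedule it cannot exist in time.

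**Step 3. What is estimable.** Write the paired difference (with minus without) as d = τ + sπ + e. Here τ is the mouthpiece effect, π is the period effect, s = +1 if the mouthpiece is second and s = −1 if it is first.

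- Fixed order: s = +1 for everyone, so the columns for τ and π are identical. The design matrix has rank 1, and only τ + π can be estimated, at any sample size.
- Both orders present: the rank is 2, and τ and π are separately estimable if there is no carryover.

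**Step 4. Illustration for the fixed order.** Assumptions, none from the documents: SD of d = 1, two-sided 5% test, n = 12, 20 or 30. The t statistic is noncentral t with n − 1 df and noncentrality (τ + π)√n. For example, with n = 20, τ = 0 and π = 0.25, the noncentrality is 0.25 × √20 = 1.12, and the test rejects 18.6% of the time.

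| Setting | n = 12 | n = 20 | n = 30 |
|---|---|---|---|
| τ = 0, π = 0.1: false positives | 6.2% | 7.1% | 8.3% |
| τ = 0, π = 0.25: false positives | 12.5% | 18.6% | 26.3% |
| τ = 0, π = 0.5: false positives | 35.3% | 56.5% | 75.4% |
| τ = 0.6, π = 0: power | 47.5% | 72.1% | 88.8% |
| τ = 0.6, π = −0.25: power | 19.8% | 31.8% | 45.8% |

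**Step 5. If order were truly randomized.** This was simulated with balanced sequences, 400,000 replicates per cell. The plain paired t-test (n − 1 df) was compared with the intercept of d regressed on sequence coded ±0.5 (n − 2 df).

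*Equal timing in both sequences.* The paired t-test does not exceed its nominal level; it becomes conservative, with about 3% false positives at π = 0.5. Power at τ = 0.6, paired versus adjusted:

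| π | n = 12 | n = 20 | n = 30 |
|---|---|---|---|
| 0 | 47.5 vs 46.8% | 72.1 vs 71.9% | 88.8 vs 88.7% |
| 0.2 | 45.7 vs 46.7% | 70.6 vs 71.7% | 87.9 vs 88.7% |
| 0.5 | 37.8 vs 46.6% | 63.3 vs 71.8% | 83.4 vs 88.7% |

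*Unequal timing.* Suppose a mouthpiece-first visit were assembled from the existing blocks. The first start is 30 + 15 + 15 + 30 + 25 = 115 minutes after the dose and the second is 115 + 45 = 160, a gap of 45 rather than 115 minutes. If the period effect is proportional to the gap, it is 0.5 in one sequence and 0.5 × 45/115 = 0.196 in the other. Both estimators are then shifted by (0.5 − 0.196)/2 = 0.15 SD. Type I error at n = 12, 20, 30 is 6.2, 8.0, 10.5% (paired) and 7.6, 9.9, 12.7% (adjusted). Randomizing order without equalizing timing therefore does not cure the problem.

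**The case against.** - **It is an exploratory pilot.** True, and this limits the weight any Aim 1 p-value can carry. The Power paragraph uses it to explain the missing power analysis. It does not excuse two incompatible accounts of how the Aim 1 data are collected.
- **Nothing in the documents sizes the period effect.** This stands. Its magnitude and direction are unknown, and the larger rows of the table are illustrations only. The aliasing itself depends on none of them.
- **The plan already guards against drift.** Medication is timed for the on phase and rest breaks are allowed (Safety and Adverse Events). These may reduce the fatigue and medication components. They leave practice, and they leave condition and period inseparable.
- **The Randomization Method section may be what is intended.** Then the schedule is unworkable as written and must change, so an edit is needed either way.
- **Randomizing order would not settle attribution.** This stands. The documents describe no sham mouthpiece and no blinded rater, so expectation and unblinded scoring would remain in the difference. That is a separate limitation, and the report should not present randomized order as removing it.
- **The fault lies in the design, not the t-test.** Largely fair. The paired t-test can be kept under either repair; what changes is what its result may be said to show.

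**Conclusion.** The concern holds. The stated randomization of mouthpiece order cannot be carried out on the stated schedule. If the schedule is followed, Aim 1's paired difference is mouthpiece effect plus period effect, and no analysis of these data can split them. That conclusion is structural and needs no assumed numbers.

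Its practical size is unknown. Under the assumptions in the working, the excess in false positives is small for a period effect of 0.1 SD, roughly two to five times nominal at 0.25 SD, and a majority of tests at 0.5 SD once n reaches 20. An opposing 0.25 SD effect cuts power by more than half at n = 12 and n = 20, and nearly in half at n = 30. Pilot status moderates the consequence, but the contradiction should be resolved before any Aim 1 result is interpreted.

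**What to change.** Reconcile the Protocol and Randomization Method sections, in one of two ways.

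**Fixed order (the only order the present schedule allows).** Delete the sentence randomizing mouthpiece order; the next sentence already covers task order. Keep the paired t-test. Add to the Statistical Analyses Plan that Aim 1 differences combine mouthpiece, practice, fatigue and time since medication, and cannot be attributed to the mouthpiece alone. The cost is one sentence removed and one added, with no new data or analysis.

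**Randomized order.** Rewrite the visit so that fabrication precedes both assessments and timing is the same in both sequences, and allocate sequence in small blocks. The paired t-test is then valid. Optionally, report instead the intercept, with 95% CI, from regressing the with-minus-without difference on sequence coded +0.5/−0.5, stating the assumptions of no carryover and an equal period effect in both sequences. This costs one degree of freedom and one line of R. In the working it gains about one point of power at a period effect of 0.2 SD and 5 to 9 points at 0.5 SD.

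As a guide to the burden, take the existing blocks with the same 25-minute sit before each assessment (an assumed arrangement). The visit becomes 15 + 15 + 30 + 25 + 45 + 25 + 45 = 200 minutes instead of 175. Assessments start 115 and 115 + 45 + 25 = 185 minutes after the dose, instead of 45 and 160. These sums allow nothing for fabrication beyond the 30-minute block. Whether such timing still serves the plan's on-phase purpose is for the investigators to judge.

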- 13) The occlusal material is adjusted at chairside so that an even continuous contact with the maxillary teeth is created on all teeth from the rear-most molar teeth including anterior teeth. The mouthpiece will then have the general appearance of a "horse shoe" in shape.
- 14) All areas which contact oral soft tissue on the perimeter of the device will be smoothed to allow placement without any trauma or discomfort to any tissue in the participant's mouth.
- 15) The mouthpiece will be placed in the participant's mouth for a period of about ten minutes to ensure there is no interference with any normal jaw and biting movements.

The mouthpiece is fabricated with polyvinyl ethylene acetate which is non-toxic to humans. There are similar mouthpieces sold over the counter by pharmacies for patient use without a physician/dentist's prescription.

Participants will be instructed to return the mouthpiece at the end of the study period.

Motor assessments

Movement Disorder Society-Unified Parkinson's Disease Rating Scale Part III (MDS-UPDRS-III) Motor subsection will be used to assess disease severity.

The GAITRite system will be used to assess gait performance. The GAITRite is a portable electronic walkway mat (600 cm long and 64 cm wide). All participants will walk along the mat so that imbedded sensors are activated by foot pressure and deactivated when pressure is released. A computer will process the footsteps for gait velocity (cm/s). The mat is located in a well-lit room, with starting and ending limits marked one meter from the mat to prevent recording acceleration and deceleration phases.

Balance will be assessed using the Mini-BESTest. The Mini-BESTest is a 14-item evaluation designed to assess a variety of balance components.

Quality-of-life questionnaires

Parkinson's Disease Questionnaire-39 (PDQ-39) contains 39 self-report items designed specifically for people with PD. There are eight subscores that are calculated along with a total score.

Parkinson's Disease Sleep Scale (PDSS) contains 15 self-report items designed specifically to assess various indicators of sleep quality in people with PD.

Participant information

Participants will fill out a demographic form, a medication form, and medical comorbidity form at the in-person visit, and note any changes in their health or medications after wearing the mouthpiece for one month.

Journal

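### Adverse events in the one-month home period, where almost all planned device wear falls, are captured only passively, with no item on falls, mouth or jaw problems, or device damage

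*Combined protocol and SAP*

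**What the plan says.** Section I (Specific Aims) asks participants to "wear it at night while they sleep and during the day, except while eating, for one month". Section III, Protocol, gives the instruction more loosely: "participants will be instructed to use the mouthpiece as much as possible for the next month". Neither states hours per day. The same section then says "Follow-up will occur one month later", and Specific Aims adds that the sleep and quality-of-life questionnaires are sent by mail. No call, visit or journal review is described in between.

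Section III, Safety and Adverse Events, states "The adverse event most likely to occur in this study is risk of falling while walking". Its safeguards are a gait belt, trained staff in close attendance, open space and rest breaks. Adverse events are to be noted in the participant's file, and for serious ones the rule is "Any serious adverse events will be reported to the local IRB immediately". The section does not say when that clock starts or how the team would hear of an event at home. For discomfort or irritation from the device, it says participants may take it out.

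Three instruments cover the home month. They are a journal (wear time, reasons for removal, optional comments), a record of changes in health or medications at one month, and an open-ended exit questionnaire completed with the Global Rate of Change Scale. The Interim Monitoring paragraph adds that data will be monitored throughout.

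**The concern.** The active safety measures work only where staff are present, while nearly all exposure to the device takes place where they are not. The protocol expects falls to be the commonest adverse event. Participants will walk at home for a month with the device in place, yet no fall question is planned for that month. The same gap applies to the problems most directly tied to a mouthpiece: oral soreness, jaw trouble and damage to the device.

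Two things are at stake. One is timeliness, because an event at home may not reach the team until the one-month forms do. The other is interpretation of Aim 2, which is partly about the feasibility of longer-term use. If participants are not all asked the same harm questions, a blank form may mean that nothing happened or that nothing was written down. A feasibility conclusion would then rest on uneven harm data.

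**Working it through.** The documents give no exposure share, adverse-event rate or sample size, so there is no stated figure to reproduce. Two checks are possible.

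**1. Share of device wear that is at home**

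Inputs:
- Wear at the visit. The Protocol section says "participants will sit with the mouthpiece in for 25 minutes" and allots 45 minutes to the motor assessment with the mouthpiece: 25 + 45 = 70 min = 1.17 h. The fabrication steps also say "The mouthpiece will be placed in the participant's mouth for a period of about ten minutes". If that fit check is separate from the 25 minutes, the total is 80 min = 1.33 h. Both are carried as *v*.
- Home wear. The duration is one month, taken as *d* = 30 days. Hours per day, *h*, are not stated and are assumed over a range of 1 to 22.

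Formula: home share = *hd* / (*hd* + *v*).

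| *h* (hours/day, assumed) | *hd* (h) | Share, *v* = 1.17 h | Share, *v* = 1.33 h |
|---|---|---|---|
| 1 | 30 | 96.26% | 95.74% |
| 2 | 60 | 98.09% | 97.83% |
| 4 | 120 | 99.04% | 98.90% |
| 8 | 240 | 99.52% | 99.45% |
| 16 | 480 | 99.76% | 99.72% |
| 22 | 660 | 99.82% | 99.80% |

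The share passes 99% when *h* > 99*v*/*d*. With *v* = 1.17 h that is 99 × 1.1667 / 30 = 3.85 h/day. With *v* = 1.33 h it is 99 × 1.3333 / 30 = 4.40 h/day. Letting the month run from 28 to 31 days widens the threshold to 3.73 to 4.71 h/day.

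So the share is above 99% for the day-and-night pattern the protocol intends, and a few points lower for a poor adherer. It is a share of wear time, not of risk.

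**2. What each instrument can yield for an event at home**

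| Instrument | When the team sees it | What is asked | Asks about falls, mouth or jaw, device damage? |
|---|---|---|---|
| Journal | No review before one month is described | Wear time, reasons for removal, optional comments | No |
| Health and medication changes | One month | Any change | Not specifically |
| Exit questionnaire | One month | Open-ended experience with the device | No |

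None is described as recording the event date, its seriousness or whether the device was in. A fall that did not lead to removal, and that the participant did not regard as a change in health, has no place where it must appear.

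The count of participants mentioning an event is therefore a lower bound with no matching upper bound, and cannot be read as a proportion of those fitted.

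**Delay.** If an event is equally likely on any of 30 days and is learned of only at day 30, the mean delay is 30/2 = 15 days and the maximum about 30, plus any postal time. This assumes that nobody contacts the team unprompted, so it describes reliance on the scheduled forms alone.

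**The case against.** The case against is substantial, and several stronger readings that a reader might infer do not hold.

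- **That adverse events are monitored only at the visit.** The journal, health-change record and exit questionnaire all reach into the home month, and the health-change item is put to every participant. The capture is passive and retrospective, but it exists.
- **That immediate reporting of serious events cannot be met.** The protocol does not say whether the clock runs from onset or from the team's awareness. If from awareness, the rule can be met. Late detection is a separate and weaker complaint.
- **That participants have no way to report a problem.** The consent form is not in the text reviewed and may give a contact route and an instruction to use it. Its absence cannot be asserted.
- **That removal is the only protection for wearing the device.** The fabrication steps trim the device so that it rests on the teeth alone, smooth its edges, and check for interference with jaw and biting movements.
- **That harms are under-counted.** This is a plausible risk of unprompted recall, not something the documents demonstrate.

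It is also fair to say that this is a small exploratory pilot, that a harm rate is not a stated aim, and that the protocol notes similar mouthpieces are sold over the counter.

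What survives is that the protocol describes no solicited adverse-event item, no adverse-event definition, no scheduled contact before one month and no clock start. A telephone number in the consent form would not supply uniform questions. The statement that data will be monitored throughout does not help either, because no home data are scheduled to arrive before one month. The reference in the safety section to close monitoring in all aspects of the study concerns staff being on hand to prevent a fall, which they cannot do remotely.

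**Conclusion.** The point holds as a weakness in how harms are ascertained, not as a breach of the reporting rule. Home harms may be under-ascertained, and detection through the scheduled forms may lag by up to about a month. Aim 2 will have no interpretable event proportion to set beside its feasibility result. The part of exposure affected is over 99% of wear if home use averages more than about 4 hours a day, and about 96% at 1 hour a day; both figures rest on assumed hours. The size of any under-count is unknown. The missing clock start and contact instruction are points to clarify, since the consent form may already cover the second. The lack of solicited questions is the substantive gap, and it is cheap to close.

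**What to change.** Add a one-page yes/no adverse-event checklist to the existing one-month forms. It should cover falls, injury, mouth or jaw problems and device damage, with the date of each event and whether the mouthpiece was in. State in the analysis plan that the number of participants with each event will be reported over all participants fitted, with the number who returned the checklist shown alongside, so that non-return is not read as absence of harm.

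As a secondary clarification, state in Safety and Adverse Events that immediate IRB reporting runs from the team's awareness of the event. Confirm that participants are told how to report home events promptly, adding an instruction only if the consent form does not already give one.

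The cost is one more page for participants and a sentence or two in the protocol. No extra visit is needed, and the planned paired t-tests do not change. The downside is that prompted questions will raise reported event counts, so the results should not be compared directly with studies that relied on spontaneous reports.
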